1 BACKGROUND INFORMATION

SHP465 is a once daily, sustained-release, single-entity mixed amphetamine salt product for oral administration. The product was previously referred to as SPD465; however, it is now being studied under the code of SHP465. The amphetamine salt combination found in SHP465 is comprised of sulfate salts of dextroamphetamine and amphetamine, with dextroamphetamine saccharate and amphetamine aspartate monohydrate, which provide a composite enantiomer ratio of 3:1 *d*-amphetamine to *l*-amphetamine.

SHP465 capsule contains 3 types of drug-releasing beads providing immediate release, pulsatile delayed release, and delayed sustained release of the mixed amphetamine salts. The immediate release bead comprises a drug-layered sphere which releases rapidly in the stomach. The pulsatile delayed-release bead includes an additional pH sensitive polymer coating which is insoluble under gastric pH conditions but is soluble above pH 5.5, thereby releasing drug in the small intestine. The delayed sustained-release bead includes a pH sensitive polymer coating with an additional coating of a sustained-release polymer; this combination begins releasing drug once the gastrointestinal track reaches pH 7.0 or above.

Amphetamines are noncatecholamine sympathomimetic amines with central nervous system stimulant activity. The primary mechanism of action is to increase synaptic concentrations of monoamine neurotransmitters, thereby indirectly enhancing noradrenergic, dopaminergic neurotransmission in the central nervous system (Heal et al., 2013). Amphetamine increases the availability of biogenic amines (primarily dopamine and norepinephrine) in central nerve synapses through multiple actions, including stimulating neurotransmitter release into the nerve terminal and inhibiting reuptake from the synapse. These actions may be the basis of its therapeutic actions in attention-deficit/hyperactivity disorder (ADHD); however, the mode of therapeutic action in ADHD is not known.

1.1 Indication and Current Treatment Options

The exact etiology of ADHD is unknown. Extensive research has suggested that neurotransmitter deficits (Arnsten, 2001), genetics (Arnsten, 2001; Brown, 2003), environment (Kahn et al., 2003), and perinatal complications (Bhutta and Anand, 2002) may all be contributing factors. The hypothesized mechanism of action of effective medications in ADHD is to raise neurotransmitter levels (specifically norepinephrine and/or dopamine, or their precursors) at the synapse either by facilitating neurotransmitter release from the synapse or by decreasing neurotransmitter reuptake by binding or activating the postsynaptic receptor (Kratochvil et al., 2003; Wang et al., 2007).

According to the Diagnostic and Statistical Manual of Mental Disorders, ADHD has 3 subtypes: hyperactive/impulsive, inattentive, and combined, and individuals with ADHD may manifest considerably different symptomology depending on sex, disorder subtype, and the presence of comorbid disorders.

Compared with nonstimulants, stimulant medications (ie, amphetamine or methylphenidate) produce the most robust improvements in symptom expression across all age ranges (Spencer et al., 1996).

Furthermore, stimulant medications have a rapid onset of action, within 1 hour to 2 hours of dosing, compared with nonstimulants (eg, atomoxetine), which can require dosing for up to 4 weeks to 6 weeks to achieve maximal therapeutic benefit ([Wilens et al., 2002](#)).

Nonpharmacologic measures (psychological, educational, and social) can also be beneficial, and psychosocial treatments for adults with ADHD have been studied ([Safren et al., 2004](#); [Greenfield and Hechman, 2005](#)). Comorbid psychiatric and learning disorders are common in adults with ADHD, and appropriate evaluation, diagnosis, and treatment are recommended ([Weiss and Murray, 2003](#)).

Importantly, symptoms may not only manifest throughout the day. Many patients continue to have residual symptoms lasting into the evening hours ([Greenfield and Hechman, 2005](#)). Adult patients may benefit from symptom relief into the evening hours for such activities as planning and organizing, or professional activities (eg, professional work at night), spousal/parental responsibilities, and driving. Similarly, impairments in nighttime activities are recognized in the pediatric population, which may need coverage all day and into the evening as well (eg, to do homework and to participate in family/social activities).

The impairments in psychosocial academic and occupational functioning associated with ADHD may arise from underlying chronic deficiencies in executive function ([Brown, 1996](#)). In general, the term executive function is used to describe a set of cognitive abilities that control and regulate judgments and behaviors which are necessary for goal-directed behavior; however, the specific definition of executive functioning varies and is debated. Understanding and treating executive functioning deficits is increasingly considered an unmet medical need in ADHD.

1.2 Product Background and Clinical Information

SHP465 and its prototypes have been evaluated in 1641 subjects in 16 clinical studies, of which 13 clinical studies were in adult subjects aged 18 years to 55 years and 3 clinical studies were in pediatric subjects aged 6 years to 17 years. The SHP465 clinical development program has shown that doses of 12.5 mg to 50 mg in adult subjects and 12.5 mg to 25 mg in pediatric subjects demonstrate a safety and efficacy comparable to the profile reflected in class labeling for stimulant products approved in the United States (US).

The pharmacokinetic (PK) profile of SHP465 is not affected if the capsule is consumed intact or if capsule contents are sprinkled onto a small amount of food (ie, 1 tablespoon of applesauce) and then ingested. The PK properties of SHP465 are not affected by sex or race. The PK properties between *d*-amphetamine and *l*-amphetamine are similar.

Acceptable safety and tolerability profiles observed were consistent with the types of side effects specified in stimulant class labeling in the US. Specifically, administration of SHP465 was associated with increases in blood pressure (mean increase approximately 2-4 mmHg) and heart rate (mean increase approximately 3-6 bpm), and treatment-emergent adverse events (TEAEs) of insomnia, decreased appetite, decreased weight, heart rate increased, and anxiety, as well as psychiatric events (eg, mania, suicidality).

Always refer to the latest version of the SHP465 investigator's brochure (IB) for the overall risk/benefit assessment and the most accurate and current information regarding the drug metabolism, pharmacokinetics (PK), efficacy, and safety of SHP465.

2 STUDY OBJECTIVES AND PURPOSE

2.1 Rationale for the Study

The proposed clinical study is being conducted to provide information on SHP465 PK, safety, and tolerability after 4 weeks of SHP465 administration at a daily dose of 6.25 mg in preschool children aged 4 to 5 years with ADHD.

2.2 Study Objectives

2.2.1 Primary Objective

To evaluate the PK, safety, and tolerability of SHP465 in children aged 4 to 5 years with ADHD after SHP465 multiple daily doses of 6.25 mg.

3 STUDY DESIGN

3.1 Study Design

The study will be a Phase 1, open-label, multiple-dose, PK, safety, and tolerability study in children aged 4 to 5 years diagnosed with ADHD. Enrollment will be stratified by gender to ensure that at least 2 of the 10 subjects expected to complete the rich PK sampling portion of the study and at least 3 of the 10 subjects expected to complete the sparse PK sampling portion of the study are females. Subjects for the rich PK sampling portion of the study will be enrolled first. Once the required number of subject is achieved, enrollment in the sparse PK sampling group will begin.

Subjects will be assessed for eligibility during the screening period. The duration of the screening period will be a maximum of 32 days. If subjects are currently taking ADHD medication, they are required to discontinue their current ADHD medication at least 7 days prior to the first dose of investigational product on Day 1 of Week 1 (washout period).

Following the screening visit, eligible subjects will return to the clinical research center (CRC) on Day 1 of Week 1 to reconfirm eligibility criteria and enter into the treatment phase.

If more than 32 days have elapsed since the screening evaluations were completed, then the following evaluations must be repeated at baseline (prior to the first dose of investigational product on Day 1 of Week 1): vital signs, clinical laboratory evaluations, blood pressure, electrocardiograms (ECGs), weight, and height. The physical examination will be abbreviated with a review of the following body systems: general appearance, respiratory, and cardiovascular.

The PK of *d*-amphetamine and *l*-amphetamine will be evaluated in this study, according to the schedule in [Table 1](#) (rich PK sample subset) and [Table 2](#) (sparse PK sample subset).

Rich PK Sample Scheme (9 Samples/Subject) Collection

Predose PK samples will be collected on Day 1 of Week 1, and serial blood samples for PK analysis will be drawn prior to dosing on Day 7 of Week 4 (within 60 minutes prior to dosing) and up to 48 hours after administration of the investigational product.

On Day 7 of Week 4, subset of subjects in the rich PK sampling portion will be required to remain at the CRC through 8 hours postdose. Following completion of the 8-hour PK sample collection, per investigator's discretion, subjects will have the option to remain at or leave the CRC. If they leave the CRC, subjects will either return to the CRC on Days 7, 8, and 9 of Week 4 for the 12-hour, 16-hour, 24-hour, and 48-hour postdose blood sample collections or, if the option is available at their clinical site, a qualified person may visit the subject for the 12-hour, 16-hour, and 24-hour postdose blood sample collections, but they must return to the clinic for the 48-hour blood sample collection.

Sparse PK Sample Scheme (4 Samples/Subject) Collection

Predose PK samples will be collected on Day 1 of Weeks 1 to 3 and on Day 8 of Week 4 (24 hours after dosing on Day 7 of Week 4) for subjects in the sparse PK sampling subset.

3.2 Duration and Study Completion Definition

Each subject's maximum duration of participation is expected to be approximately 9 weeks. The study will be completed in approximately 12 months.

- Screening period:
 - A maximum of 32 days before the first dose of investigational product
 - If applicable, this includes a washout period that is to start 7 days before the first dose of investigational product.
- Treatment Period: Total duration for the treatment period is approximately 30 days for subjects in the rich PK sampling portion of the study and 29 days for subjects in the sparse PK sampling portion of the study.
- Follow-up contact: At the last clinic visit, subjects and their parent/legally authorized representative (LAR) will be offered to rollover into the SHP465-308 study. If subjects agree and their parent/LAR signs the informed consent form, this will end their participation in the SHP465-112 study. If they do not want to participate in the SHP465-308 study, follow-up contact will be conducted approximately 1 week (7 days [± 2 days]) following the last dose of investigational product.

The Study Completion Date is defined as the date the final subject, across all sites, completes their final protocol-defined assessment. Please note that this includes the follow-up visit or contact, whichever is later. The Study Completion Date is used to ascertain timing for study results posting and reporting.

3.3 Sites and Regions

The study will be conducted in approximately 10 sites in the US.

4 STUDY POPULATION

Each subject and parent/LAR must participate in the informed consent/assent process, and the parent/LAR must provide written informed consent/assent before any procedures specified in the protocol are performed.

4.1 Inclusion Criteria

The subject will not be considered eligible for the study without meeting all of the following criteria (including test results):

1. Subject is a male or female aged 4 years to 5 years inclusive at the time of consent.
2. Subject and parent/LAR are willing and able to fully comply with all of the testing and requirements defined in the protocol. Specifically, the parent/LAR must be available at approximately 8:00 AM (± 1 hour) to administer the dose of investigational product at the time points specified in the protocol.
3. Subject's parent/LAR must sign the informed consent form, and there must be documentation of assent (if applicable) by the subject in accordance with the International Council for Harmonisation (ICH) Good Clinical Practice (CGP) Guideline E6 (2016) and any updates, and applicable regulations, before starting any study-related procedures.
4. Subject satisfies the following ADHD criteria during the screening period:
 - Meets the Diagnostic and Statistical Manual of Mental Disorders, Fifth Edition (DSM-5) criteria for a primary diagnosis of ADHD (any subtype) based on a detailed psychiatric evaluation using the Mini International Neuropsychiatric Interview for Children and Adolescents (MINI-KID)
 - Has an ADHD Rating Scale-5 (ADHD-RS-5) Child, Home Version Total Score of ≥ 28 for boys and ≥ 24 for girls
 - Has a Clinical Global Impressions-Severity of Illness (CGI-S) score ≥ 4 .
5. Subject functions at an age-appropriate level intellectually, as determined by the investigator.
6. Subject has undergone an adequate course of nonpharmacological treatment **OR** the subject has a severe enough condition to consider enrollment without undergoing prior nonpharmacological treatment, based on the investigator's judgment **OR** has never taken ADHD medication **OR** has taken ADHD medication with unacceptable efficacy and/or tolerability.
7. Subject has the ability to take investigational product by either swallowing the capsule whole or sprinkling the capsule contents in applesauce and ingesting the entire mixture immediately without chewing.
8. Subject has lived with the same parent/LAR for at least 6 months.

4.2 Exclusion Criteria

Subjects are excluded from the study if any of the following exclusion criteria are met:

1. Prior enrollment or participation in the study.
2. Subject has a documented allergy, hypersensitivity, or intolerance to amphetamine or to any excipients in the investigational product.
3. Subject cannot swallow a pill and/or applesauce, or has an allergy to applesauce.
4. Subject is currently taking or has taken ADHD medication with acceptable efficacy and tolerability.
5. Subject has taken ADHD medication within 7 days prior to the administration of investigational product.
6. Subject has used any medication (including over-the-counter, herbal, or homeopathic preparations) within 30 days prior to the administration of investigational product or 5 half-lives, whichever is longer, with the exception of the following:
 - Thyroid medication
 - Intermittent use of nonsteroidal anti-inflammatory drugs or acetaminophen for minor aches and pains
 - As needed use of a beta-agonists inhaler for mild asthma or exercise induced bronchospasm
 - Over-the-counter nonsedating antihistamines such as fexofenadine (ALLEGRA[®], Sanofi), loratadine (CLARITIN[®], Schering-Plough), or cetirizine hydrochloride (ZYRTEC[®], McNeil-PPC) for allergies.
 - Subject has continuously used oral corticosteroids ≥ 7 days in 3 months prior to investigational product dosing. If continuous use was < 7 days, 1 month of washout prior to dosing of investigational product is required.
7. Within 30 days prior to the administration of investigational product:
 - Subject has used an investigational product.
 - If the elimination half-life of the previous study's investigational product was less than 6 days, then the last dose of the previous investigational product should be 30 days prior to the first dose of SHP465.
 - If the elimination half-life of the previous study's investigational product was greater than 6 days, then the last dose of the previous investigational product should be 5 half-lives prior to the dose of SHP465.
8. Subject has glaucoma.
9. Subject has a known family history of sudden cardiac death or ventricular arrhythmia.

10. Subject has a known history of symptomatic cardiovascular disease, structural cardiac abnormality, cardiomyopathy, serious heart rhythm abnormalities, or other serious cardiac conditions placing them at increased vulnerability to the sympathomimetic effects of a stimulant drug.
11. Subject has any clinically significant ECG or clinically significant laboratory abnormalities at the first screening visit based on the investigator's judgment. A single retest of laboratory parameters is allowed based on the investigator's judgment.
12. Subject has Marfan's syndrome.
13. Subject has a blood pressure \geq 95th percentile for age, sex, and height at the screening visit ([Appendix 2.3](#) and [Appendix 2.5](#)).
14. Subject has a height \leq 5th percentile for age and sex at the first screening visit ([Appendix 2.2](#) and [Appendix 2.4](#)).
15. Subject has a weight \leq 5th percentile for age and sex at the first screening visit.
16. Subject has current abnormal thyroid function test results, defined as abnormal thyroid-stimulating hormone, thyroxine (T4), and tri-iodothyronine (T3) at the first screening visit. Treatment with a stable dose of thyroid medication for at least 3 months is permitted.
17. Subject has a history of seizures (other than infantile febrile seizures).
18. Subject has a current, controlled (requiring medication or therapy) or uncontrolled, comorbid psychiatric disorder including but not limited to any of the following comorbid Axis I disorders and Axis II disorders:
 - Post-traumatic stress disorder or adjustment disorder
 - Bipolar illness, psychosis/schizophrenia, or positive family history of these disorders in first- or second-degree relatives
 - Pervasive developmental disorder
 - Obsessive-compulsive disorder
 - A serious tic disorder, or a family history of Tourette disorder
 - Substance abuse or dependence disorder
 - Any other disorder that, in the opinion of the investigator, contraindicates SHP465 or amphetamine treatment or confounds efficacy or safety assessments.
19. Subject is currently considered a suicide risk in the opinion of the investigator, has previously made a suicide attempt, or has a prior history of or is currently demonstrating active suicidal ideation.
20. Subject has a history of physical, sexual, or emotional abuse.
21. Subject has a primary sleep disorder (eg, sleep apnea, narcolepsy).
22. Subject has a history or is currently diagnosed with an eating disorder.

23. Subject has a clinically important abnormality on the urine drug and alcohol screen (excluding the subject's current ADHD stimulant, if applicable) at the first screening visit.
24. Subject lives with anyone who currently abuses stimulants or cocaine, based on the investigator's judgment.
25. Subject has a concurrent chronic or acute illness (such as severe allergic rhinitis or an infectious process requiring antibiotics), disability, or other condition that might confound the results of safety assessments conducted in the study or that might increase risk to the subject.
26. Subject has any additional condition(s) such as any significant illness or unstable medical condition that, in the investigator's opinion, would prohibit the subject from completing the study and /or could lead to difficulty complying with the protocol.

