- λ_z The first order rate constant associated with the terminal phase of elimination

There will be no inferential statistical analysis of the PK data. Summary descriptive statistics (number of observations, mean, standard deviation, coefficient of variation, median, maximum, minimum and geometric mean) will be determined for all PK parameters. Plasma concentrations at each nominal sampling time will also be summarized using descriptive statistics.

Safety Endpoints

Safety will be assessed by treatment-emergent AEs (TEAEs), vital signs (systolic and diastolic blood pressure, pulse rate, respiratory rate, and body temperature), 12-lead ECGs, weight, height, clinical laboratory tests (biochemistry, hematology, and urinalysis), Post Sleep Questionnaire (PSQ), and a validated sleep questionnaire (Children's Sleep Habits Questionnaire [CSHQ]).

Additionally, the Columbia-Suicide Severity Rating Scale (C-SSRS) scale will capture the safety of SHP465 related to suicidality.

The safety endpoints will be summarized with descriptive statistics for the safety set.

Baseline is defined as the last assessment prior to the first dose of investigational product. Potentially clinically important findings will also be summarized or listed. The potentially clinically important values will be defined in the statistical analysis plan.

Weight, height, BMI, vital signs, ECG, PSQ, and CSHQ will be summarized. The C-SSRS results will be summarized and a listing of the C-SSRS data will be provided for subjects with a positive response.

Adverse events will be coded using the agreed-upon version of the Medical Dictionary for Regulatory Activities. The number of events, incidence, and percentage of TEAEs will be calculated overall, by system organ class, and by preferred term. Treatment-emergent AEs will be further summarized by severity and relationship to investigational product. Adverse events related to investigational product, AEs leading to withdrawal, SAEs, and deaths will be similarly summarized/listed.

STUDY SCHEDULE

Table 1: Schedule of Assessments for Rich Pharmacokinetic Sampling Portion

Assessment Day	Screening and Washout		Week 1 to 3		Week 4								Follow-up ^a		
	D -32 to D -8	D -7 to D -1 Washout	D 1	D 2-7	D 1	D 2-6	D 7					D 8 ^b	D 9 /ET ^b		
Treatment Week 4 Time Point (h)						Predose ^c	0	2	5	8	12	16	24	48	
Informed Consent & Assent	X														
Inclusion/Exclusion Criteria	X		X ^d												
Demographics	X														

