7.2.2.6 Drug and Alcohol Screen

A urine screen for drugs of abuse and alcohol will be performed at the time point shown in [Table 1](#) (rich PK sample subset) and [Table 2](#) (sparse PK sample subset). Additional drug and alcohol screens may be performed at the investigator's discretion.

Urine samples are to be tested for amphetamines, barbiturates, benzodiazepines, cannabinoids, cocaine, methadone, opiate metabolite, and phencyclidine.

Results of urine drug and alcohol screens will be reviewed and verified by the study monitor, but will not be collected in the CRF database.

Any positive result for drugs of abuse or alcohol at the first screening visit (with the exception of the subject's current stimulant therapy) will exclude the subject from further participation in the study.

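### Exclusion 6's 30-day bar on any medication does not except ADHD drugs, so exclusion 5's 7-day rule is redundant and conflicts with the planned 7-day washout; a corticosteroid exclusion sits among the exceptions

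*Protocol*

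**What the plan says.** Protocol Section 4.2 makes each exclusion sufficient on its own.

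- **Exclusion 5:** "Subject has taken ADHD medication within 7 days prior to the administration of investigational product".
- **Exclusion 6:** "Subject has used any medication (including over-the-counter, herbal, or homeopathic preparations) within 30 days prior to the administration of investigational product", lengthened to five half-lives where that is longer, with five bulleted exceptions. Four are drug classes: thyroid medication, intermittent anti-inflammatory drugs or acetaminophen, as-needed beta-agonist inhalers, and over-the-counter nonsedating antihistamines. None is ADHD medication.
- **Fifth bullet of exclusion 6:** it opens "Subject has continuously used oral corticosteroids" and specifies 7 days or more in the 3 months before dosing. It then says of shorter use that "1 month of washout prior to dosing of investigational product is required".

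The washout is described elsewhere. Section 3.2, repeated in the synopsis, says of the screening period that "this includes a washout period that is to start 7 days before the first dose of investigational product". Tables 1 and 2 have a column headed "D -7 to D -1 Washout". Sections 3.1 and 7.1.1 have children on ADHD medication stop it at least 7 days before the first dose. Table 3 gives psychostimulants and amphetamines a 7-day minimum, and gives clonidine, guanfacine and noradrenaline reuptake inhibitors 30 days. The urine drug screen allows for a stimulant at the first screening visit: "excluding the subject's current ADHD stimulant, if applicable" in exclusion 23 and "with the exception of the subject's current stimulant therapy" in Section 7.2.2.6.

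The synopsis repeats exclusions 5 and 6, including the corticosteroid bullet.

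**The concern.** A 7-day window for ADHD drugs inside a window of at least 30 days for all drugs does nothing. Either exclusion 5 is surplus, or exclusion 6 lacks an exception. The rest of the protocol points to the second.

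Sites have two ways to go wrong. One that applies exclusion 6 literally delays or excludes a child whom the 7-day washout was designed to admit. Eligibility is reconfirmed on Day 1, and Section 7.1.1 does not allow a definite screen failure to be rescreened, so a child who has completed the 7-day washout could be lost for good. A site that follows the washout text instead doses a child who meets an exclusion, which is an eligibility deviation. With about 10 sites and about 24 children, readings may differ between sites.

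The corticosteroid bullet fails in the opposite direction. As an exception it admits children with prolonged recent use, while those with shorter use must wait a month.

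**Working it through.** The plan gives no figure of its own here, so the check compares look-back windows.

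**Set-up.** Assume there is no Day 0, so a last dose on Day -k lies k days before Day 1. The protocol does not say whether a dose exactly 7 or 30 days before counts as inside the window, so both readings are shown.

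**1. Redundancy.** Exclusion 5 covers 7 days. Exclusion 6 covers the larger of 30 days and five half-lives; the second exceeds 30 only if the half-life exceeds 30 / 5 = 6 days. Since 7 < 30, every child who meets exclusion 5 already meets exclusion 6.

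**2. Stimulant doses on which the two criteria disagree.**

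| Reading | Passes exclusion 5 | Passes exclusion 6 | Passes 5 but meets 6 | Length |
|---|---|---|---|---|
| Strict | k > 7 | k > 30 | Day -8 to Day -30 | 30 - 8 + 1 = 23 days |
| Looser | k ≥ 7 | k ≥ 30 | Day -7 to Day -29 | 29 - 7 + 1 = 23 days |

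**3. Earliest dosing after stopping.** Strict: 8 days under exclusion 5, 31 under exclusion 6, and 31 - 8 = 23 days later. Looser: 7 and 30, and 30 - 7 = 23 days later.

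**4. Repeat evaluations.** Section 3.1 requires vital signs, laboratory tests, ECG, weight and height again if more than 32 days have passed since screening. Let the child stop s days after the screening evaluations.

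- Strict, exclusion 6: s + 31 > 32, so s ≥ 2. Strict, exclusion 5: s + 8 > 32, so s ≥ 25.
- Looser: s + 30 > 32, so s ≥ 3; and s + 7 > 32, so s ≥ 26.

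Repeat bloods add 2 mL biochemistry + 1 mL hematology = 3 mL (Section 7.2.2.5). Against Section 7.2.4, the rich subset goes from 24-33 mL to 27-36 mL and the sparse subset from 14 mL to 17 mL.

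**5. Which texts conflict.** A child whose washout starts on Day -7 took the last dose about 7 or 8 days before Day 1. That is always inside 30 days, so the child always meets exclusion 6. This is a direct conflict with Section 3.2, the matching synopsis line and the washout column. The at-least-7-days wording of Sections 3.1 and 7.1.1 and the Table 3 minimum are floors that a 30-day stop also satisfies, so they show the intended period without being contradicted.

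**6. Corticosteroids.** Read literally, the bullet lifts exclusion 6 for continuous use of 7 days or more. Even without that exception, exclusion 6 reaches back only 30 days when five half-lives are shorter than that. The intended 3 months is about 90 days, so about 90 - 30 = 60 days of look-back are stated in no other criterion (59 to 62 days for calendar spans of 89 to 92 days). Section 5.2.1 prohibits oral corticosteroids during the study and gives no 3-month look-back.

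All of these are calendar days. The documents do not say how many children fall in them.

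**The case against.** The best defense is that the specific rule governs the general one. Exclusion 5 is about ADHD drugs and exclusion 6 about drugs in general. Sections 3.1 and 7.1.1 and Table 3 all point to 7 days, and Section 7.1.1 states the 7-day rule before referring to Section 4.2. Section 3.2 is a duration summary that does not name ADHD medication. The corticosteroid bullet is phrased like an exclusion, so its purpose is clear, and exclusion 25 lets an investigator keep out a child whose illness might confound safety or raise risk. A deviation removes nobody from the safety or PK set; SAP Section 6 only reviews, summarizes and lists deviations.

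Much of this stands. The specific-over-general reading is probably what was meant, but no text states it, and the rule that any one criterion excludes works against it. Exclusion 25 reaches some steroid-treated children only at the investigator's discretion and not by steroid exposure.

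Four stronger readings are tempting and not supported:

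- A reader might infer that exclusion 23 and Section 7.2.2.6 contradict exclusion 6. They concern the first screening visit, which can be as early as Day -32, so a child on a stimulant then can still be 30 days off it by Day 1.
- A reader might count the 14-day Table 3 row for herbal preparations as a further conflict. Table 3 gives minimums, and 30 days meets that one, as it does the 7-day rows.
- A reader might infer an extra needle stick from the repeat laboratory tests. Both subsets already give a predose PK sample on Day 1, so the 3 mL can be drawn then.
- A reader might infer damage to the PK results. The rich profile follows about 28 days of dosing, so a stimulant dose before the washout does not materially affect it.

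**Conclusion.** The point holds as an eligibility drafting error that should be corrected. Exclusion 6 as written leaves exclusion 5 with nothing to do and conflicts with Section 3.2, its synopsis copy and the washout column. For stimulants the two criteria disagree over 23 calendar days, whichever way the boundary days are read consistently. The corticosteroid bullet, taken literally, exempts the use it is meant to exclude.

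The practical effect is limited. Exclusion 4 removes children well served by ADHD medication and exclusion 2 removes documented amphetamine intolerance, so the number affected is probably small, but it is unknown. Sample size, Week 4 PK and the planned analyses do not change.

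The conclusion rests on the protocol dated 15 Sep 2017. SAP Section 1 cites an administrative change dated 31 Oct 2017 that is not among the documents; whether it touched this text is unknown.

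**What to change.** 1. **Exclusion 6:** add the exception 'ADHD medication, which is governed by exclusion 5 and Table 3'. Leave other drug classes under exclusion 6.
2. **Exclusion 5:** refer to the Table 3 period for the drug's class: 7 days for psychostimulants and amphetamines; 30 days for clonidine, guanfacine and noradrenaline reuptake inhibitors. Without this pointer, the new exception would leave a flat 7 days for drugs to which Table 3 gives 30.
3. **Corticosteroids:** move the bullet to its own exclusion, covering continuous oral use of 7 days or more in the 3 months before dosing, or shorter use without 1 month of washout.
4. **Synopsis:** make the same edits.

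Table 3 needs no change. The cost is a wording amendment with the sponsor and IRB/EC approval that Section 10.3.2 already requires. Visits, sample size and SAP analyses stay as they are. Check the 31 Oct 2017 administrative change first, in case part of this is already done.
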